**Table 2.1: Schedule of Events**

ASSESSMENTS AND EVENTS*	SCREENING/ BASELINE a	TREATMENT PERIOD						
		MONTH 2 (WEEK 8) VISIT (± 5 DAYS) †	MONTH 4 (WEEK 16) VISIT (± 5 DAYS) †	MONTH 6 (WEEK 24) VISIT (± 5 DAYS)	MONTH 12 VISIT (WEEK 48) (± 2WEEKS)	MONTH 18 VISIT (WEEK 72) (± 2WEEKS)	MONTH 24 (WEEK 96) OR EARLY TERMINATION VISIT (± 2WEEKS) ‡	SAFETY FOLLOW UP (+ 5 DAYS) m
SAFETY ASSESSMENTS (ALL SUBJECTS)								
INFORMED CONSENT	X							
MEDICAL HISTORY	X							
INTERVAL HISTORY b	X	X	X	X	X	X	X	
PHYSICAL EXAMINATION c	X	X	X	X	X	X	X	
VITAL SIGNS	X	X	X	X	X	X	X	
HEMATOLOGY, CHEMISTRY PANEL, URINALYSIS	X	X	X	X	X	X	X	
PREGNANCY TEST	X	X	X	X	X	X	X	
CONCOMITANT MEDICATIONS	X	X	X	X	X	X	X	X
SUICIDAL IDEATION AND BEHAVIOR (C- SSRS) d	X	X	X	X	X	X	X	
ADVERSE EVENTS	X	X	X	X	X	X	X	X
PHARMACODYNAMIC ASSESSMENTS (ALL SUBJECTS)								
BIOMARKERS: CK, FREE SERUM SA, AND BIOMARKERS OF SIALYLATION AND OTHER BIOMARKERS e	X	X	X	X	X	X	X	
FREE, TOTAL AND BOUND URINE SA LEVELS f	X	X	X	X	X	X	X	
URINE TEST FOR MANNAC g	X	X	X	X	X	X	X	

ASSESSMENTS AND EVENTS*	SCREENING/ BASELINE a	TREATMENT PERIOD						
		MONTH 2 (WEEK 8) VISIT (± 5 DAYS) ‡	MONTH 4 (WEEK 16) VISIT (± 5 DAYS) ‡	MONTH 6 (WEEK 24) VISIT (± 5 DAYS)	MONTH 12 VISIT (WEEK 48) (± 2WEEKS)	MONTH 18 VISIT (WEEK 72) (± 2WEEKS)	MONTH 24 (WEEK 96) OR EARLY TERMINATION VISIT (± 2WEEKS) †	SAFETY FOLLOW UP (+ 5 DAYS) m
TREATMENT DISPENSING AND COMPLIANCE (ALL SUBJECTS)								
TREATMENT DISPENSED h	X	X	X	X	X	X		
TREATMENT COMPLIANCE		X	X	X	X	X	X	
EFFICACY ASSESSMENTS (UX001-CL202 AND UX001-CL301 SUBJECTS)i								
DYNAMOMETRY	X	X	X	X	X	X	X	
6-MINUTE WALK TEST (6MWT)	X	X	X	X	X	X	X	
SIT-TO-STAND TEST	X	X	X	X	X	X	X	
WEIGHTED ARM LIFT TEST	X	X	X	X	X	X	X	
GNE MYOPATHY FUNCTIONAL ACTIVITIES SCALE (GNEM-FAS)	X	X	X	X	X	X	X	
INDIVIDUALIZED NEUROMUSCULAR QUALITY OF LIFE QUESTIONNAIRE (INQOL)	X	X	X	X	X	X	X	
EFFICACY ASSESSMENTS (UX001-CL203 SUBJECTS)								
DYNAMOMETRY j	X			X	X	X	X	
GNEM-FAS k	X			X	X	X	X	
SHORT FORM HEALTH SURVEY-36 (SF-36)	X			X	X	X	X	

\* Refer to study-related materials for recommended timing and order of assessments to be administered at each study visit.

- ‡ Subjects who roll-over from the UX001-CL203 study will not have a Month 2 or Month 4 visit. Assessments at these visits will only be performed for subjects who roll-over from the UX001-CL202 and UX001-CL301 studies. UX001-CL202 subjects will complete the same efficacy assessments as the subjects who rollover from UX001-CL301.
- a. Potential subjects can be screened up to 5 days after the last dose on the parent study. Baseline Visit should be not be more than 5 days after Screening visit. Subjects can have a concurrent Screening and Baseline visits. Study drug will be dispensed only after all study procedures at the Baseline Visit have been performed. For subjects who discontinue prior to completing the study, every reasonable effort should be made to perform the Early Termination (ET) procedures within four weeks of discontinuation.
- b. Interval history will include any signs, symptoms, or events (i.e. falls) experienced by the subject since the prior study visit that are not related to study procedure(s) performed at prior study visits or study drug. Interval history may include exacerbation or improvement in existing medical conditions (including the clinical manifestations of GNEM) that might interfere with study participation, safety, and/or positively or negatively impact performance of functional assessments.
- c. The physical examinations at Baseline/Screening, including a neurological examination; all others will be brief physical examinations. If a patient is unable to stand or has significant postural issues that interfere with collection of a standing height, self-reported adult height should be captured.
- d. Baseline C-SSRS administered at Baseline/Screening visit (may be same as last visit in parent study). Since Last Visit C-SSRS administered at all subsequent visits.
- e. Serum will be obtained at all study visits to evaluate creatine kinase (CK), serum SA and potential biomarkers of sialylation, and other markers of muscle injury and remodeling.
- f. Blood samples, preferably pre dose, and first-morning void urine will be collected to assess trough SA levels; record volume of urine collected.
- g. An aliquot from first morning void urine will be used for assessment of ManNAc; record volume of urine collected.
- h. Subjects should be instructed to return unused study drug and packaging to every visit. Note that all subjects being treated with 12 g/day Ace-ER in UX001-CL202 will be transitioned to 6 g/day Ace-ER dose in this protocol.
- i. For UX001-CL202 subjects, assessments that cannot be safely performed by a subject due to disease progression should not be administered.
- j. For subjects enrolling from UX001-CL203, lower extremity muscle strength for knee extensors muscle group only.
- k. For subjects enrolling from UX001-CL203, the GNEM-FAS Expanded version will be used.
- l. The Early Termination Visit occurs if a subject discontinues prior to completing the study or no longer wants to participate in the study. Every reasonable effort should be made to have subjects return to the clinic within 4 weeks of discontinuation and perform the Early Termination procedures; however, subjects who are unable to return to the clinic will be given the option of having an Early Termination Visit telephone call within 4 weeks of discontinuation from study, where appropriate information will be collected by the clinical site.
- m. Safety Follow-up visit to be conducted by phone 30 days (+5 days) after last dose of study drug.

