## 5 INTRODUCTION

The product under investigation is sialic acid (SA) administered in extended release (Ace-ER) tablets. Ace-ER is intended for use as a substrate replacement therapy for the treatment of GNE Myopathy (GNEM), also known as Hereditary Inclusion Body Myopathy (HIBM), Quadriceps Sparing Myopathy (QSM), Inclusion Body Myopathy type 2, Distal Myopathy with Rimmed Vacuoles (DMRV), and Nonaka myopathy ([Huizing et al. 2009](#)); ([Jay et al. 2009](#)); ([Malicdan et al. 2008](#)). Currently there are no approved treatments for GNEM.

SA is an essential, naturally occurring amino sugar found in humans and most organisms. Defects in the SA biosynthetic pathway cause GNEM, a severe progressive myopathy. By replacing SA substrate, sialylation should be restored on key target glycoproteins and glycolipids, leading to restoration of biochemical function, improved muscle physiology and improved clinical function. The scientific rationale is primarily based on the nature of the underlying genetic defect supported by proof of concept work in a knockout mouse that models the muscle disease and pathology of HIBM ([Malicdan et al. 2009](#)). The safety of SA has been studied in chronic treatment studies in HIBM mice and toxicology studies in multiple species of normal animals. These data demonstrated reasonable safety for SA and established a no adverse effect level (NOAEL) of 2,000 mg/kg in rats and dogs, enabling clinical studies in GNEM patients.

Ultragenyx has developed Ace-ER tablets since successful use of SA replacement therapy in humans is believed to depend upon optimized exposure to the compound. SA has a half-life of less than 1 hour in the circulation ([Malicdan et al. 2009](#)). Ace-ER was developed to improve the stability of exposure to SA and allow more appropriate dosing and efficient substrate replacement. The Ace-ER formulation was evaluated in an initial Phase 1 study to establish the safety and pharmacokinetic (PK) profile of a single dose and 7 days of repeat dosing in SA-deficient GNEM patients. The study drug was well tolerated at all dose levels. There were no serious adverse events (SAEs), and all adverse events (AEs) were mild to moderate with no dose relationship or pattern.

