### **7.5.3 Drug Concentration Measurements**

The concentration of free SA in serum will be measured to further characterize the PK of Ace-ER. At the Baseline Visit and each subsequent visit a serum sample will be collected, preferably, prior to the morning dose of study medication (pre-dose) to assess trough levels of free SA.

The free, total, and bound urine SA levels (corrected for creatinine) will reflect the absorption of SA and the incorporation into sialylated proteins and oligosaccharides during treatment with Ace-ER tablets. The change in urine SA levels will be analyzed the same as for the primary endpoint. At Baseline/Screening, and each clinic visit, first-morning void urine will be collected (pre-dose) to assess trough levels; the volume obtained will be recorded.

Collection and processing instructions can be found in the Laboratory Manual.

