8.6 Efficacy Analysis

Efficacy analyses will use generalized estimating equation (GEE) (Hanley et al. 2003) to evaluate trends over time with respect to the changes from baseline for all continuous efficacy endpoints. Baseline will be included as a covariate in the model. GEE will be the primary analysis method for all repeated measures endpoints. The statistical analyses will be reported in summary tables, figures, and data listings. Statistical tests will be 2-sided at the alpha=0.05 significance level.

Efficacy analysis will be based on the full analysis set.

Additional efficacy analyses may be performed for subjects enrolled in CL301 by incorporating data from both the parent study and the current study to compare the placebo versus UX001 treatment groups using the methodology described in ([Hu et al. 2007](#)). Such analyses examine the extended treatment effect of UX001 on the placebo subjects who now are taking UX001 in the extension study.

Parent study baseline will be used to evaluate the long-term study drug effect from the parent study drug administration, except for subjects enrolling from CL202.

Current study baseline will be used to evaluate the continuous long-term study drug effect going on after the parent study.

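### Continuing subjects may have been off drug for 0 to 10 days when the CL302 baseline sample is taken, so their change from baseline in free serum sialic acid depends partly on visit timing

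*Protocol*

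**What the plan says.** Footnote a to Protocol Table 2.1, repeated in SAP Appendix 10.5, sets the handover from the parent study. It opens with "Potential subjects can be screened up to 5 days after the last dose on the parent study". It then recommends a limit of 5 further days between Screening and Baseline, and lets the two visits fall on the same day. On supply, it adds this condition: "Study drug will be dispensed only after all study procedures at the Baseline Visit have been performed".

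Protocol 7.5.3 places the first SA sample at that visit: "At the Baseline Visit and each subsequent visit a serum sample will be collected". It asks for the sample, as a preference, "prior to the morning dose of study medication (pre-dose) to assess trough levels of free SA". Protocol 7.6.5 then analyses change from baseline in serum and urine SA at trough by GEE.

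SAP 4.1.2 lists change from baseline in free serum SA and in urine SA as drug-concentration endpoints. SAP 5.1 defines the current study baseline as the last value before the first CL302 dose, with no condition on the time since the last parent-study dose. For efficacy, SAP Table 8.1.1 adds a parent study baseline for CL301 and CL203. For biomarkers it gives the current study baseline only.

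On pharmacology, Protocol section 5 states that "SA has a half-life of less than 1 hour in the circulation". Protocol 5.2.3 gives a time to peak of about 3 to 10 hours after Ace-ER. Protocol 5.2.4 puts free serum SA on 6 g/day at about twice the healthy-volunteer level.

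**The concern.** Two subjects can take 6 g/day in the parent study, take it again throughout CL302, and have identical exposure at every CL302 visit. If one has a concurrent Screening and Baseline the morning after the last parent dose, the baseline is an on-drug trough. If the other is screened on day 5 and has Baseline on day 10, the baseline is an off-drug level. The plan labels both values as baseline and averages the two changes.

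What is at stake is the meaning of the free serum SA change endpoint in continuing subjects. The synopsis says this change will reflect absorption during treatment. That holds if every reference value is off drug. If every reference value is on drug, the change instead measures whether exposure was maintained. With a mixture in unknown proportion, the cohort mean answers neither question.

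This is a separate matter from combining former-placebo and active CL301 subjects in one biomarker group. The mixture here arises among subjects who were already on Ace-ER.

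**Working it through.** The documents state no total gap and no expected SA change, so there is no plan figure to reproduce. The steps below use the documents' inputs and label each assumption.

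**1. Permitted gap.** Gap = (last parent dose to Screening) + (Screening to Baseline).
- Minimum: 0 + 0 = 0 days, because the visits may be concurrent.
- Maximum: 5 + 5 = 10 days. The second limit is worded as a recommendation.
- CL302 supplies no drug to cover the interval.

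**2. Drug-derived SA left after the gap.** Residual r = 0.5^(24 × days / half-life in hours). The documents support a half-life of 1 hour at most for circulating SA. The values of 4, 8 and 12 hours are assumptions that allow for slow release from the tablet.

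| Half-life | 1 day | 2 days | 5 days | 10 days |
|---|---|---|---|---|
| 1 h | 0.000006% | about 0 | about 0 | about 0 |
| 4 h | 1.6% | 0.02% | about 0 | about 0 |
| 8 h | 12.5% | 1.6% | 0.003% | about 0 |
| 12 h | 25% | 6.25% | 0.1% | about 0 |

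Most of the loss comes in the first day or two. The effect is close to a step between on-drug and off-drug rather than a gradient over 10 days.

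**3. Change from baseline for one subject on 6 g/day before and after rollover.** Let T be the on-drug level at sampling and E the untreated level. Baseline = E + (T − E) × r, so change = (T − E) × (1 − r).
- Gap 0 (ordinary trough, r = 1): change = 0.
- Gap of 5 to 10 days (r at most 0.001): change = T − E, the full increment.

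For scale, set the healthy-volunteer level to 1 and T = 2 (Protocol 5.2.4, assumed to apply at trough). Assume E between 0.5 and 1.0, which the documents do not give. Then T − E runs from 2 − 1.0 = 1.0 to 2 − 0.5 = 1.5 times the healthy level. Relative to baseline that is 1.0/1.0 = +100% to 1.5/0.5 = +300%.

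**4. Cohort mean.** If a share g of these subjects has a washed-out baseline, mean change = g × (T − E). The shares below are illustrative.

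| g | Mean change as share of full increment | In healthy-level units |
|---|---|---|
| 10% | 10% | 0.10 to 0.15 |
| 30% | 30% | 0.30 to 0.45 |
| 50% | 50% | 0.50 to 0.75 |

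On-treatment exposure is identical in all three rows.

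**5. Who is exposed to the window.** Protocol 7.6.1 plans 55 + 80 + 30 = 165 subjects. All CL202 and CL203 subjects come from open-label Ace-ER: 55 + 30 = 85 of 165. The CL301 active arm adds to this, but the CL301 allocation is not stated. SAP 3.5 expects about 180 subjects and gives no split, so the protocol's numbers are used.

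**The case against.** The case on the other side is strong on scope, and most of it stands.

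- **Frequency.** The documents show what is permitted, not what happens. Concurrent visits are allowed, and footnote d lets the baseline C-SSRS coincide with the last parent visit, so same-day rollover was clearly foreseen. Ten days is the extreme case. This stands: the share g is unknown.
- **Visit scheduling rather than treatment.** A reader might infer that the SA change reflects scheduling and not treatment. The documents do not support that. The rise after a gap is a drug effect; timing decides how much of it appears as change. CL202 subjects moving from 12 to 6 g/day also have a real dose change, so zero is not their expected change even without a gap.
- **Number affected.** A reader might add an active-arm share of CL301 and arrive at 125 (85 + 40) or 138 (85 + 53) subjects. That needs an allocation of 1:1 or 2:1, which the documents do not give. It also counts everyone to whom the window applies as having had a gap.
- **Size.** The 2-fold figure describes levels during 6 g/day dosing and is not stated to be a trough. If overnight pre-dose levels are lower, T − E is smaller. The zero-versus-full contrast remains, but its size in these units is an assumption.
- **Urine SA.** Bound and total urine SA reflect incorporation into sialylated proteins and oligosaccharides. The documents give no turnover time for these, so the circulating half-life cannot be carried over.
- **Maintained exposure and compliance.** A reader might conclude that the study cannot show maintained exposure, or that compliance estimates are distorted. SA is measured at every clinic visit, so on-treatment levels can be followed without a baseline. Protocol 7.4.7 refers to trough levels, not changes, and SAP 8.5.2 computes compliance from dosage taken.
- **Baseline as a covariate.** The general GEE description (Protocol 7.6.4, SAP 8.6) includes baseline. If it is applied to SA, it lets change vary with baseline level, but it neither identifies which baselines were on drug nor corrects the descriptive mean change.

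None of this removes the core point. The SAP takes one reference value for all, and that value can be either an on-drug or an off-drug level.

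**Conclusion.** The point holds for change from baseline in free serum SA among subjects already on Ace-ER. The 0 to 10 day range is exact from the text. The near-complete loss of drug-derived SA after several days follows from the stated half-life, and survives an assumed effective half-life of up to 12 hours (0.1% left at 5 days). For a subject on 6 g/day throughout, the expected change is about zero from an on-drug trough and about the full increment after a multi-day gap. That increment is +100% to +300% of baseline if trough SA is twice the healthy level and untreated SA is 0.5 to 1.0 of it; both are assumptions.

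The window applies to 85 of the 165 planned subjects plus the CL301 active arm, of unstated size. How many will have a gap cannot be told from the documents. The conclusion does not extend to urine SA, on-treatment SA levels, compliance or the primary endpoint. It is a correction the SAP should make, limited to one drug-concentration endpoint.

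**What to change.** In SAP 5.1 and Table 8.1.1:

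1. Derive the time from the last parent-study dose to the baseline SA sample, in hours where times were recorded, using the last-dose date in the parent database.
2. For subjects continuing on Ace-ER, classify the baseline as an on-drug trough only if it is a pre-morning-dose sample following a dose the previous evening or at bedtime. A cut-off of one day would be too loose: by the table above, a sample at 24 hours may retain anywhere from almost none to 25% of drug-derived SA.
3. Report free serum SA change separately for on-drug and later baselines, with the number of subjects in each.
4. For continuing 6 g/day subjects, add change from the last on-treatment parent-study sample as the reference for maintained exposure. SAP Appendix 10.4 lists serum SA at the final week of each parent study: Week 156 in CL202, Week 48 in CL301 and Week 48 in CL203.
5. Show CL202 subjects coming from 12 g/day separately, since their parent sample was taken at a different dose.
6. Present urine SA by gap descriptively only. For CL202, Appendix 10.4 lists urine SA only at Weeks 0 and 12, so no late parent reference exists there.

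The cost is SAP wording and a few derived variables from data the sponsor should already hold. The downside is that parent-study and CL302 samples may have been assayed in different batches, which should be noted beside the added comparison. No visit window or treatment rule changes.

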**Drug Concentration Measurements:**

Serum Free Sialic Acid: The change in free SA level in serum (trough) will reflect the absorption of SA during treatment.

Urine Sialic Acid - Free, Total and Bound: The urine SA level (corrected for creatinine) will reflect the absorption of SA and the incorporation into sialylated proteins and oligosaccharides during treatment.

Urine Testing for ManNAc: Urine will be tested for the presence of ManNAc to detect compliance with prohibited medication restrictions.

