#### ***Phase 1 Pharmacokinetic and Safety Study (UX001-CL101):***

The exposure of aceneuramic acid in adult GNEM patients was characterized in study UX001 CL101 following single (fasted and fed) and repeat doses of Ace-ER up to 6000 mg/day for 7 days. The PK parameters derived from traditional non-compartmental analysis are presented in UX001-CL101 following single dose administration (fasted and fed states) and repeat dosing (steady state). Following single oral administration of Ace-ER (fasted or fed), the maximum baseline-adjusted SA concentration in serum was achieved in approximately 3 to 10 hours. The Cmax increased in a less than dose proportional fashion across the dose range studied, showing a 2.7-fold increase between the 650 mg and 6000 mg dose groups.

Observed results from single-dose administration demonstrate that adequate absorption of the drug, with or without food, occurs at all dose levels. The impact of food on exposure is complex with some dose levels showing higher AUC with fasted conditions (650 mg and 4875 mg dose), similar AUC under both fasted and fed conditions (2925 mg dose), and higher AUC with food (1950 and 6000 mg dose). For the 6000 mg dose, the AUC was significantly greater (~46%) when administered in the fed state at 3.934 mcg\*hr/ml compared with 2.592 mcg\*hr/ml fasted. Given that the 6000 mg dose was administered using the 500 mg tablet, the differences observed may be due to a subtle effect of the larger tablet size on the absorption rate and/or duration, even though in vitro dissolution data is comparable for the 325 mg and 500 mg tablets. The larger tablet may have a longer time of release in vivo. This difference coupled with a food effect prolonging aceneuramic acid exit from the stomach may enhance the overall absorption of aceneuramic acid (acidity should improve aceneuramic acid absorption by neutralizing its charge).

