#### **7.6.5 Analyses of Drug Concentration Measurements**

The SA analysis set will be used to evaluate free serum SA levels and urine SA levels (free, bound and total; corrected for creatinine) at trough (pre-dose) using the SA analysis set. Changes from baseline will be analyzed using the GEE method for repeated measures analysis.

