6 ANALYSIS SETS

Three analysis sets are defined for the study.

Full Analysis Set: The full analysis set will include all subjects with a CL302 baseline measurement and at least one post-baseline measurement in CL302. This set will be used for the efficacy analysis.

Safety Analysis Set: The safety analysis set consists of all subjects who receive at least one dose of study drug in CL302. This set will be used for safety analysis.

Sialic Acid Analysis Set: The SA analysis set will consist of all subjects with evaluable free serum SA levels in CL302.

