Week 96 /ET efficacy analysis	Full Analysis Set	CL203	Ace-ER 6 g/day	Parent Study Baseline	
			Ace-ER 6 g/day	Current Study Baseline	
Week 96/ET safety analysis	Safety Analysis Set	CL301	Placebo*	Current Study Baseline	
			Ace-ER 6 g/day		
			All		
		CL202	Ace-ER 6 g/day		
		CL203			
		Total			
Week 96/ET analysis on biomarkers	Sialic Acid Analysis Set	CL301	Ace-ER 6 g/day	Current Study Baseline	
		CL202			
		CL203			
		Total			

* This refers to the enrolled subjects who had received placebo treatment in parent study CL301.

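### Serum sialic acid is to be analysed at trough, but the SAP has no rule to set apart post-dose samples or, for serum and urine, off-drug early-termination samples

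*Protocol*

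**What the plan says.** - **Target of the analysis.** The Protocol synopsis states: "The change in free SA level in serum (trough) will reflect the absorption of SA during treatment". Protocol 7.6.5 evaluates free serum SA and "urine SA levels (free, bound and total; corrected for creatinine) at trough (pre-dose) using the SA analysis set", and models changes from baseline by GEE.
- **Blood timing.** Protocol Table 2.1, footnote f: "Blood samples, preferably pre dose, and first-morning void urine will be collected to assess trough SA levels". Section 7.5.3 repeats the preference for serum. Section 7.5.5.5 says in a single sentence both that pre-dose blood is preferred and that samples are taken before study drug is given.
- **Urine timing.** Section 7.5.3 specifies a first-morning void, pre-dose, and does not soften this to a preference.
- **Early termination.** Table 2.1 schedules SA sampling in one column shared by Week 96 and ET. Footnote a says "every reasonable effort should be made to perform the Early Termination (ET) procedures within four weeks of discontinuation". Footnote l lets subjects who cannot return have a telephone visit instead.
- **SAP.** Section 4.1.2 defines the endpoints as changes from baseline in serum free SA and urine SA, with no trough or on-drug condition. Section 6: "The SA analysis set will consist of all subjects with evaluable free serum SA levels in CL302"; the term evaluable is not defined. Section 7.2.5 uses nominal visits without windows. Table 8.1.1 has a row for "Week 96/ET analysis on biomarkers", against the current-study baseline. Section 1 gives the SAP precedence over the protocol on analysis methods.

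**The concern.** The protocol names a specific quantity, the trough level on treatment, but neither the collection rule for blood nor the SAP ensures that the analysed values are that quantity. Protocol 7.5.6 reads free serum SA as absorption and exposure of muscle, and 7.4.7 says trough levels may also help to estimate compliance. A subject who takes the morning dose before the clinic visit can look better exposed than at trough. A compliant subject sampled some weeks after stopping can look as though no drug had been taken. The two errors run in opposite directions and depend on appointment time and dropout, so a plausible mean would not reveal them.

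**Working it through.** **No plan figure to reproduce.** The documents give no sample size, SD, expected change, dropout rate or share of post-dose samples for any SA endpoint. The calculations below are illustrations on stated assumptions.

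**Step 1: which samples are exposed (post-baseline).**

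| Departure from trough | Serum | Urine | Visits |
|---|---|---|---|
| Drawn after the morning dose | permitted | not permitted as written | any |
| Drawn off drug | possible | possible | ET only |

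**Step 2: is a post-dose sample different?** In the Phase 1 study, after a single dose, "the maximum baseline-adjusted SA concentration in serum was achieved in approximately 3 to 10 hours". A sample drawn after the morning dose may therefore lie on the rise to the peak. The post-dose/trough ratio is not given. It is uncertain because, with a bedtime dose (Protocol 7.4.1), the pre-morning level may not be the true minimum.

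**Step 3: is a late ET sample off drug?** Protocol section 5: "SA has a half-life of less than 1 hour in the circulation". Residual fraction = 0.5^(time/half-life).
- Half-life 1 h (the documents' upper bound): 0.5^24 = 6 × 10⁻⁸ after one day.
- Half-life 24 h (assumed, to allow generously for extended release): 0.5^1 = 50% at 1 day, 0.5^5 = 3% at 5 days, 0.5^28 = 4 × 10⁻⁹ at 28 days.

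A four-week ET sample is an off-drug value on either assumption. One taken a day after the last dose might not be.

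**Step 4: effect of off-drug values on change from baseline.** Let T be the on-drug trough, B the off-drug level and e the share of Week 96 values that are off drug. The visit mean is T − e(T − B). Take T = 2 and B = 1. The 2-fold ratio is borrowed from Protocol 5.2.4, which compares treated levels with healthy volunteers, so here it is an assumption.

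| e (assumed) | Visit mean | Change if baseline off drug (true +1) | Change if baseline on drug (true 0) |
|---|---|---|---|
| 5% | 1.95 | +0.95 | −0.05 |
| 10% | 1.90 | +0.90 | −0.10 |
| 20% | 1.80 | +0.80 | −0.20 |

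The absolute shift, −e(T − B), is the same in both columns; its meaning is not. Both kinds of baseline can occur. Former placebo subjects from CL301 enter untreated, while the others come from active treatment. Footnote a allows screening up to 5 days after the last parent-study dose and Baseline up to 5 days after that.

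**Step 5: adding post-dose serum values.** Let p be the share of post-dose samples among the rest and r the post-dose/trough ratio. Mean = (1 − e)[(1 − p)T + p·r·T] + e·B. All of e, p and r are assumed.
- Post-dose only, p = 10–30%, r = 1.25–2.0: mean 2.05 to 2.60, so the increment over B is overstated by 5% to 60%.
- Both, e = 5–20%: the error in the increment runs from −16% (e = 20%, p = 10%, r = 1.25: 0.8 × 2.05 + 0.2 = 1.84) to +52% (e = 5%, p = 30%, r = 2: 0.95 × 2.60 + 0.05 = 2.52).
- Near-cancellation, e = p = 10%, r = 1.5: mean 1.99, an error of −1%. The mixing alone still contributes a between-subject SD of √(0.81 × 0.01² + 0.09 × 1.01² + 0.10 × 0.99²) = 0.44 on a trough of 2.

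**The case against.** **Week 96/ET may only name the final analysis.** The label heads the efficacy, safety and biomarker rows of SAP Table 8.1.1, and in Appendix 10.1 it heads a column covering every visit. The efficacy templates in Appendix 10.7 end at Week 96, although none is for SA. This stands as an ambiguity. The shared column in Table 2.1 and the use of nominal visits point towards pooling, and on either reading no rule keeps out an off-drug value.

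**The restriction may already be there.** Protocol 7.6.5 says trough, the word evaluable could be used to screen samples, and collection details sit in a Laboratory Manual that is not among the documents. But an undefined term is not a prespecified rule, and the SAP, which prevails on methods, carries no trough condition. The objection does establish that the documents permit mixing without showing that it happens or how often.

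**Little depends on it.** Planned compliance is dosage taken over dosage planned (SAP 8.5.2). SA is not the primary endpoint. The only SAP method listed for serum SA by name is exploratory summary statistics for CL203 subjects (Appendix 10.1). This stands and limits the importance: no primary safety or muscle-strength conclusion rests on it.

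**Conclusion.** The gap is real and limited. Followed as written, the plan lets post-dose serum values in at any visit and off-drug serum and urine values in at ET, and reports the result under a trough heading. Its size cannot be given from the documents; the figures above rest on assumed shares, an assumed post-dose ratio and a borrowed 2-fold level.

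A reader might infer more than this, and the documents do not support it:
- **That all SA measures mix post-dose values.** Urine is first-morning void and pre-dose.
- **That every visit mean is contaminated by off-drug samples.** Only ET values are. Four weeks is the outer target, and a telephone ET visit gives no sample.
- **That the drug effect is understated by a fixed percentage, such as 10% to 30%.** Such a figure only restates an assumed off-drug share. It fits subjects whose baseline was off drug; for those whose baseline was on drug, the error is an apparent decline from a true change near zero.

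The change is worth making because the bias is avoidable at small cost, but it concerns the drug-concentration analysis only.

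**What to change.** Add a sample-level rule to the SAP's data-handling section; section 6 defines sets of subjects, not samples.

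1. Trough summaries and the GEE model use post-baseline serum samples documented as drawn before the next dose and within one normal dosing interval, for example the morning after the previous bedtime dose. This keeps a valid ET sample taken the next morning, which a blanket exclusion of samples after the last dosing day would lose.
2. Apply the same on-drug condition to urine.
3. Classify samples by the recorded last-dose date, with dose and sampling times where available. Do not use the last-dose date imputed under SAP 7.2.1 for this purpose, since a dosing-visit date can long precede the true last dose.
4. Do not assign off-drug ET samples to Week 96. List post-dose and off-drug samples separately and show an all-samples sensitivity table.
5. State whether Week 96/ET is a pooled visit or the name of the final analysis, and reconcile the two timing statements in Protocol 7.5.5.5.

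**Cost.** SAP wording, plus dose and sampling times on the CRF if not already recorded. Some samples leave the trough summary. Samples without recorded times can be handled only in the sensitivity table, and new CRF fields cannot recover times for samples already drawn.
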